To assess the effectiveness of this multilevel intervention, called the workplace *Metabolic Health Improvement Program (MHIP)*, we will conduct a double-randomized trial in partnership with the clinical trials division of a large Northern California-based academic healthcare system, Sutter Health ($N=700$ employees on $N=16$ hospital campuses). We will first cluster-randomize 8 Sutter Health hospital campuses to the SSB sales ban condition and 8 campuses to serve as controls (no sales ban). Across these 16 campuses, we will further randomize heavy-SSB-consuming employees (>30 oz/week) to receive a brief SSB counseling intervention delivered remotely or to a control condition.^{11,12} The **primary outcomes** are central obesity (e.g., waist circumference) and change in serum insulin sensitivity (homeostatic model assessment [HOMA] ratio). **Secondary outcomes** include changes in SSB consumption, Body Mass Index (BMI), and lab values to include: lipid profile, triglycerides, triglyceride:HDL ratio, uric acid, ApoA, ApoB, lactate, ALT/AST, GGT, fasting glucose, fasting insulin, HbA1c. We will assess dietary composition remotely using the Automated Self-Administered 24-hour (ASA-24) at baseline, 6 and 12 months, and waist circumference remotely with empirically validated instructions and a standardized tape measure provided to participants. We will collect blood samples in the workplace labs at baseline and 12 months. All analyses will consider compensatory changes in at-home SSB intake, calories from sugar, and total calories. Aims are:

Aim 1: How well does each intervention work alone? We will assess the independent effects of the brief counseling intervention and workplace SSB sales ban on changes in primary and secondary outcomes. We will compare outcomes across employees exposed to the brief intervention only ($n=175$), SSB sales ban only ($n=175$), and no intervention ($n=175$). *We hypothesize that the brief counseling intervention and sales ban will each independently decrease waist circumference and HOMA relative to no intervention. Those at high risk (baseline BMI >25 , ethnic-minority, and lower-occupational status) will benefit more from the interventions.*

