2. I felt joyful, glad, happy.
3. I felt in control, coping well, on top of things.
4. I felt sad, downhearted, unhappy.

Scale:

0 = Not at all

1 = A little bit

2 = Somewhat

3 = Moderately

4 =Extremely

Consumption Battery – Evening, last item administered – Supplement

1. Thinking back on how much sugary drinks you had **today**, which is most true for you:

Response options: Assessment 1 (baseline)

- I drank less than I usually do
- I drank about as much as I usually do
- I drank more than I usually do

Response options: Assessment 2 and beyond
(1-month post-Ban and all further assessments)

**SUTTER HEALTH
INSTITUTIONAL REVIEW BOARD**

Protocol Summary Form

- I drank less than I usually did before the Sweet study
- I drank about as much as I usually did before the Sweet study
- I drank more than I usually did before the Sweet study

Self-Efficacy Battery – Morning

If going to work:

1) How sure are you that you will avoid drinking sugary drinks today while at your Sutter Health workplace?

Not sure at all ----- Extremely sure

Sliding bar, slider starting at middle or optimally nowhere and it gets placed when the respondent touches the screen, if starting in the middle then movement of bar required to advance to next question

- Don't know
- I don't plan to go to my Sutter Health workplace today

2) How sure are you that you will avoid drinking sugary drinks today while **not** at your Sutter Health Workplace?

[1] Not sure at all

[2]

[3] Somewhat sure

[4]

[5] Extremely sure

- I do not drink sugary drinks
- Don't know

Blood Draw

The orders for the blood draw will be signed off by [name] the study physician. Results will be sent to patients via My Health Online. The study participants will be asked to review out of range labs with their primary care physician

(4c) Methods of Data Analysis:

Analysis Plan for Aim 1: *How well does each intervention work alone?* We will assess the independent effects of the brief counseling intervention and workplace SSB sales ban on changes in primary and secondary outcomes.

Introduction: Aim 1 analyses will compare primary and secondary outcomes for employees exposed to the brief intervention only, the SSB sales ban only, and no intervention. Our operative hypothesis is that both the brief counseling intervention and sales ban will independently decrease HOMA and waist circumference relative to no intervention. Of four smaller studies testing the effects of brief SSB

**SUTTER HEALTH

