INSTITUTIONAL REVIEW BOARD**

Protocol Summary Form

counseling interventions, all found decreases in SSB consumption and BMI.⁴¹⁻⁴⁴ A pilot study and current trial by this team found that workplace sales bans reduce SSB consumption, waist circumference and some blood biomarkers for metabolic disease.¹¹

Analyses for all aims will also consider the hypothesis that those at highest risk for obesity and metabolic disease will benefit more from the interventions. This is justified by our pilot study showing that employees with a baseline BMI <25 benefitted most from the sales ban and brief intervention.¹¹ Preliminary studies (described above) suggest that ethnic minority and lower occupational status employees may experience disproportionate reductions in SSB consumption following an employer sales ban.

Analyses for all aims will also consider the possibility that study participants exposed to the interventions could compensate for reduced SSB consumption during work hours by increasing their consumption of SSBs at home, or by increasing calories from sugary foods or in the total diet.^{107,108} In our evaluation of the UCSF sales ban, we observed no compensatory at-home SSB consumption but rather, spillover effects of the intervention: After 12 months of exposure to a sales ban, the average SSB intake of heavy drinkers not only declined at work but also by 40% at home (by 9.3 oz/day) (data unpublished).

Research Design for Aim 1: The main analysis will focus on ANOVA and regression modeling to determine the independent effects of each intervention on primary and secondary outcomes.

Key Measures for Aim 1: As described in section C3d above: HOMA, waist circumference, abdominal adiposity, SSB consumption, insulin sensitivity, BMI, lipid profile, triglycerides, triglycerides:HDL ratio, liver function, glucose control, demographics, risk factors/disparities, and intervention assignment.

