Analytic Plan: We will analyze Aim 1 using all data collected at the baseline, 6- and 12-month time points. First, we will use ANOVA to compare group means and determine whether there is a significant main effect for each intervention (the sales ban and the brief intervention). Based on theory and our previous studies, we know that baseline risk factors and demographics are likely relevant to the impact of these interventions; those at greater baseline risk tend to benefit more from the interventions. Therefore, each dependent variable will also be examined using a linear regression model, which allows us to observe the main effects of these factors. For example, the model predicting HOMA change would include assignment to the sales ban condition (coded as 0/1), assignment to the brief intervention condition (coded as 0/1), baseline HOMA, baseline SSB consumption, baseline BMI, race/ethnicity, and sex. Subsequent models can consider baseline BMI > 25, ethnicity and job classification. The procedure for analyzing each outcome would be the same, but with each primary and secondary outcome substituted for HOMA in turn.

For SSB consumption, we will examine at-work consumption, at-home consumption, and total consumption as separate outcomes to thoroughly investigate the impact of the interventions across work and home environments. We will similarly check for potential compensatory consumption in sugar from calories and total calories for participants in the intervention conditions relative to controls. If ASA-24-based total calories or calories from sugar disproportionately increase in the intervention groups, this suggests a compensatory effect.

Although we believe our strategy of cluster randomization and controlling for individual differences that can vary regionally (such as ethnic distribution) is sufficient, we will also analyze the effects of the brief intervention via an exploratory mixed regression model, with individuals nested within sites, to see if study site was an important factor. If it is, we will consider mixed models where possible.

**SUTTER HEALTH
INSTITUTIONAL REVIEW BOARD**

Protocol Summary Form

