Power Calculations: Power calculations are based on changes observed in the pilot study and response rates from the current Sutter Health trial. Calculations are conservative, based on 80% retention of participants after 12 months. With an initial N of 700 drawn from 16 Sutter Health sites randomly assigned to the sales ban and control conditions, and with participants within those sites randomly assigned to brief intervention/no brief intervention conditions, 80% retention would result in an overall N of 550 at 12 months. This results in approximately 138 in each of four experimental conditions: brief intervention + sales ban, the brief intervention only, sales ban only, and no intervention. Power analysis for a full factorial design conducted with the BDEsize¹⁰⁹ package within R¹¹⁰ indicates that with 80% power and an alpha level of .05, we will be able to detect effect sizes as small as .08 for the effect of each intervention on each outcome.

Anticipated Problems and Alternative Approaches: One potential problem is attrition, particularly biased attrition. We have calculated the sample to allow for up to 20% attrition; this is a conservative number based on our current Sutter Health data. In the UCSF pilot, which took place entirely pre-pandemic, we achieved a 94.4% response rate for blood draws. The existing study team has experience with the challenges of retaining a sample of health care workers during a challenging time and can use the same techniques (e.g., email and phone outreach) to reduce attrition here. We will conduct statistical tests to determine if attrition is biased on baseline risk levels, demographic factors (including regional differences), or study condition.

As with all self-report data, the survey data on SSB consumption could be biased, perhaps particularly for intervention participants who want to self-present improvement. However, the anthropometric and blood measures are objective and should show a consistent pattern with the SSB changes. Standard data cleaning procedures should reveal any extreme cases of self-representation bias. For SSB consumption data, we have also established a convention in previous studies of pruning outliers that are more than 4 SD away from the mean to reduce error from participants who may have responded inaccurately.

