We have several primary and secondary outcomes. To avoid bias from multiple statistical tests, we will closely examine patterns of data. Many of the biomarkers are related, for example, as are the anthropometric measurements. Thus, it will be apparent whether or not each result is consistent with the overall pattern of health impacts.

Expected Outcomes: We expect statistically significant main effects for both study condition variables in the ANOVA analysis, specifically that the means for each of the three groups exposed to the sales ban and/or brief interventions will demonstrate more improvement (reduction in HOMA, abdominal adiposity, blood lipids, SSB consumption, BMI, etc.) than those in the group receiving neither intervention. We also anticipate statistically significant coefficients for each study condition variable in the regression analysis that again indicates that those interventions are linked to better outcomes. This would indicate that each intervention has an effect.

Analysis Plan for Aim 2: *Does a multilevel intervention work better?* We will assess the multilevel effects of combining a brief intervention and SSB sales ban on outcomes.

Introduction: The goal of Aim 2 is to test the hypothesis that the combined intervention will have a greater effect on outcomes than the brief intervention or sales ban alone. This is justified by our pilot study findings that employees benefitted most from the multilevel intervention (see Figure 1)¹¹ and by

**SUTTER HEALTH
INSTITUTIONAL REVIEW BOARD**

Protocol Summary Form

the socioecological model which argues that obesity prevention should address multiple levels of intervention at once.⁹⁹

Research Design for Aim 2: The analysis will use ANOVA and regression models similar to those above, but with the key addition of an interaction term for the two interventions, allowing us to explore the possibility that they work better in combination than separately.

Key Measures for Aim 2. Measures are the same as those described above under Aim 1.

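### No deciding test is named for the primary outcomes: each intervention effect is tested by an ANOVA with no baseline covariate and again by a baseline-adjusted regression

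*Combined protocol and SAP*

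**What the plan says.** The primary outcomes, in section 1, are "central obesity (e.g., waist circumference) and change in serum insulin sensitivity" (HOMA). Section 4c then describes two analyses of each intervention on each outcome.

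- Aim 1, Analytic Plan, first step: "First, we will use ANOVA to compare group means and determine whether there is a significant main effect for each intervention". No covariate is named, and the response (12-month value, change, or repeated measures) is not defined.
- Same paragraph, second step: "each dependent variable will also be examined using a linear regression model". The example model for HOMA change contains both 0/1 assignment indicators plus "baseline HOMA, baseline SSB consumption, baseline BMI, race/ethnicity, and sex", and the outcome is swapped in turn.
- Aim 1, Research Design: "The main analysis will focus on ANOVA and regression modeling to determine the independent effects of each intervention". The two methods are named side by side, with no ranking.
- Aim 1, Expected Outcomes: "We expect statistically significant main effects for both study condition variables in the ANOVA analysis". Significant regression coefficients are anticipated as well, and the two together are taken to show that each intervention works.
- Aim 2, Analytic Plan: the same pair is repeated with an interaction term added to each.

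Alpha appears only in the power paragraphs ("with 80% power and an alpha level of .05"). The one provision for multiple testing is to look closely at patterns across outcomes.

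**The concern.** Both analyses test the same null hypothesis for the same outcome and can give different p-values. The plan does not say which one decides, whether one or both must be significant, or what follows if they disagree. The choice could therefore be made after the results are seen, and a reader of the results could not rule that out.

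Two things are at stake, under different decision rules. If the ANOVA decides, the trial gives up precision that its own planned regression would deliver. If either result can be cited, the error rate for a single effect on a single outcome goes above .05 before any multiplicity across outcomes. The ambiguity also reaches Aim 3, which treats the total intervention effect as already established by these analyses.

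**Working it through.** **The plan's own figures.** 700 × .80 = 560, against the stated 550; the gap is small. 550 / 4 = 137.5, which gives the stated 138 per cell. With N = 550, two-sided alpha .05 (sidedness is not stated), 80% power, no covariates and no clustering, the smallest detectable 1-df effect in a 2×2 design is Cohen's f = .120. The .12 stated for the interaction reproduces as f. The .08 stated for main effects does not reproduce under the variants tried: power is 47% if it is f and 15% if it is d. Nothing below depends on the .08.

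**Inputs for the comparison.** Let r be the correlation between the baseline and 12-month values of an outcome. The documents do not give it, so .5 to .9 is assumed. Also assumed are equal variance at the two times, independent observations, and adjustment for the outcome's own baseline only.

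**Residual variance**, in units of the 12-month variance:
- ANOVA on 12-month values: 1
- ANOVA on change: 2(1 − r)
- Baseline-adjusted regression: 1 − r²

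The ratio of adjusted to ANOVA variance is therefore (1 + r)/2 for change and 1 − r² for 12-month values.

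**Power of the ANOVA where the adjusted model has 80%:** Φ(2.80 × √ratio − 1.96), with 2.80 = 1.96 + .84. At r = .7:
- Change: 2.80 × √.85 = 2.58; 2.58 − 1.96 = .62; Φ = 73%.
- 12-month value: 2.80 × √.51 = 2.00; 2.00 − 1.96 = .04; Φ = 52%.

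**Type I error per hypothesis.** Under the null the two test statistics are approximately bivariate normal with correlation √ratio. P(either significant) = 1 − P(both |Z| < 1.96), and P(both significant) = .10 − P(either).

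| r | Power, change ANOVA | Power, 12-month ANOVA | Either test, change | Either test, 12-month | Both tests, change | Both tests, 12-month |
|---|---|---|---|---|---|---|
| .5 | 68% | 68% | .073 | .073 | .027 | .027 |
| .7 | 73% | 52% | .068 | .083 | .032 | .017 |
| .8 | 76% | 39% | .065 | .088 | .035 | .013 |
| .9 | 78% | 23% | .060 | .092 | .040 | .008 |

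A simulation of 20,000 null trials of 548 participants at each r gave either-test rates of .059 to .074 (change) and .073 to .093 (12-month value), in agreement.

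**By decision rule:**
- ANOVA decides: error .05, power as in columns 2 and 3.
- Either suffices: error above .05, adjusted-model power kept.
- Both required: error below .05, power no higher than the ANOVA's.
- Regression alone decides: error .05 and the adjusted model's full power.

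**Which response is likelier.** Aim 1 is framed as "independent effects of the brief counseling intervention and workplace SSB sales ban on changes in primary and secondary outcomes", and Expected Outcomes speaks of improvement in group means. Both point to change scores. For HOMA, with blood drawn only at baseline and 12 months, the group-by-time test of a repeated-measures ANOVA is the same as a change-score ANOVA.

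**The case against.** The strongest reply is that the better analysis is already in the plan. The baseline-adjusted regression is named as part of the main analysis, so it is not a side look at risk factors, and no power is lost if it is the one relied on. The plan also never says that either test suffices. Expected Outcomes can be read as wanting the two to agree, in which case error is below .05. A change-score ANOVA does use the baseline, and at r = .9 it costs only two points of power. All of this stands, and it limits the point to the missing decision rule.

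Two further objections also stand. First, section 4b (Participant Randomization) puts the enrolment measurements before the individual counselling randomisation, but no section puts them before campus allocation, and section 1 has campuses randomised first. A reader might infer that baseline precedes randomisation for both interventions; the documents show it only for counselling. Second, the figures above assume independent observations. They suit counselling best and do not carry over to the sales ban, allocated to 16 campuses, if outcomes correlate within campus. The main regression has no site term, so naming it as it stands would not give a valid confirmatory test of the ban.

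None of this supplies the missing rule. Agreement between the tests is expected, but it is not stated as a requirement.

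**Conclusion.** The point holds in this form: for each intervention effect on each primary outcome, and again for the Aim 2 interaction, two tests are planned and neither is named as deciding. Of the four possible rules, only naming the baseline-adjusted regression alone gives both a .05 error rate and that model's full power.

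The size is modest on the likelier reading. A change-score ANOVA has 68% to 78% power where the adjusted model has 80%, and either-test error is about .06 to .07. It is larger if the ANOVA is run on 12-month values: power 68% down to 23%, either-test error .07 to .09. These ranges rest on an assumed r of .5 to .9 and on independent observations.

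A reader might infer that the plan both loses power and inflates error, or that its error rate already exceeds 5%. The documents do not support either statement. The two harms belong to different rules, the plan adopts none of them, and error exceeds .05 only if either result may be cited. Even then it is not .10, because the two tests are strongly correlated.

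**What to change.** 1. State that the single confirmatory test of each intervention effect on each primary outcome is its coefficient in the baseline-adjusted model at 12 months: the outcome's own baseline value plus the listed covariates, with the list fixed in advance (Aim 2 adds job classification only if numbers allow).
2. Apply the same rule to the Aim 2 interaction coefficient.
3. Report ANOVA group means descriptively, without p-values, and define their response and time point.
4. For the sales ban and the interaction, make the confirmatory model account for site. The plan already lists a mixed model with individuals nested in sites, but as exploratory and for the counselling effect; it would need to be extended and promoted, with a stated method for inference from 16 campuses.
5. State when baseline is measured relative to campus allocation and the start of the ban.

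Items 1 to 3 cost only wording, since the data and model are already planned. Item 4 costs somewhat more: a model specification, and a power statement for the ban and interaction that allows for clustering. Item 5 is a sentence. None of this settles multiplicity across the two primary outcomes and several effects, which needs its own rule.

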Analytic Plan for Aim 2: Having established the main effects of each intervention under Aim 1, our analyses for Aim 2 focus on the interaction between them. Specifically, we anticipate that the combined intervention will have an effect above and beyond the simple additive effects of the two interventions. This analysis will require replicating the ANOVA and regression models used for Aim 1 with the addition to each of an interaction term for the two interventions. For example, the model predicting HOMA change will include assignment to the sales ban condition (coded as 0/1), assignment to the brief intervention condition (coded as 0/1), the interaction term for the two conditions (sales ban*brief intervention), baseline HOMA, baseline SSB consumption, baseline BMI, race/ethnicity, job classification (if sample size allows, as above), and sex. The procedure for analyzing each outcome is the same, but with each primary and secondary outcome substituted for HOMA in turn. This time, the main variable of interest will be the interaction term. We will graph and deconstruct each significant interaction term to determine the details of the interaction.

Power Calculations: As with Aim 1 above, power calculations are based on findings from the UCSF pilot and retention rates from the Sutter pilot. We will have 175 participants in each of the following groups. With 80% retention, this allows a final N of 550, with approximately 138 in each of the four experimental conditions. Power analysis for a full factorial design conducted with the BDEsize¹⁰⁹ package within R¹¹⁰ indicates that at 80% power and an alpha level of .05 we will be able to detect effect sizes as small as .12 for the interaction between the two interventions.

Anticipated Problems and Alternative Approaches: As with Aim 1, attrition and self-report bias are the primary potential issues we anticipate; handling of each is described above.

Expected Outcomes: We anticipate a significant interaction term, and more specifically, that the effect of the sales ban and brief intervention together will be stronger than each is individually. Participants assigned to the brief intervention and working at sites with a sales ban would thus demonstrate the greatest amount of change, and more change than one would expect if the effect of the two conditions were simply additive.

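### Aim 1 asks what each intervention does alone, but its four-cell main effects add half of the interaction that Aim 2 expects

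*Combined protocol and SAP*

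**What the plan says.** **The question.** Section 1 (Aim 1) and the Introduction to the Aim 1 analysis plan in section 4c ask how well each intervention works alone. The comparison is among "employees exposed to the brief intervention only, the SSB sales ban only, and no intervention". The hypothesis is that "both the brief counseling intervention and sales ban will independently decrease HOMA and waist circumference relative to no intervention". These are two contrasts, each against the cell that receives neither intervention.

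**The analysis.** The Aim 1 Analytic Plan uses ANOVA to "determine whether there is a significant main effect for each intervention (the sales ban and the brief intervention"). It then fits a linear regression with a 0/1 term for the ban, a 0/1 term for counselling and baseline covariates. There is no product term.

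**The conclusion drawn.** Aim 1, Expected Outcomes, anticipates significant main effects and significant regression coefficients, and adds: "This would indicate that each intervention has an effect".

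**The expectation for Aim 2.** The Analytic Plan for Aim 2 anticipates that "the combined intervention will have an effect above and beyond the simple additive effects of the two interventions". Its models come from "replicating the ANOVA and regression models used for Aim 1 with the addition to each of an interaction term". The interaction is named as the main variable of interest, and it is broken down only where it is significant.

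**The concern.** A factorial main effect averages an intervention's effect over both levels of the other factor. It equals the effect alone only when the two interventions do not interact, and the plan expects them to interact. The Aim 1 estimates would then not measure what Aim 1 asks.

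This matters to an employer thinking of adopting one component. It also matters to the trial's rationale: section 3 (Significance) says that the pilot could not test counselling without a ban. An estimate that draws half its information from the ban campuses does not fill that gap by itself.

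**Working it through.** **Inputs.** From Aim 1, Power Calculations: 700 enrolled, 80% retention, 550 at 12 months, about 138 in each of four cells, alpha .05, 80% power, detectable effect .08. From Aim 2, Power Calculations: detectable effect .12 for the interaction. From section 2, Pilot Study of Multilevel Intervention: SSB reductions of 25.4 oz (combined) and 8.2 oz (ban only). Assumed: two-sided tests, equal cells, a common SD and, unless stated, independent errors.

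**1. The plan's own figures.** 700 × 0.80 = 560, close to the stated 550; 550/4 = 137.5. For any one-degree-of-freedom effect in a balanced 2×2 with N = 550, the detectable Cohen's f at 80% power is 0.120 (d = 2f = 0.239). The stated .12 reproduces as f (power 80.2%). The stated .08 does not: power is 46.5% if it is f and 15.3% if it is d. The nearest reading is f/√2 = 0.085. No scale is named, so I do not call .08 wrong, and nothing below depends on it.

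**2. Which cells enter Aim 1.** All four. Its power statement is for a full factorial with four conditions. Its expected outcomes cover three exposed groups. Aim 2 adds an interaction term to the same models, and three cells could not estimate one.

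**3. What the coefficient estimates.** Let C and B be the effects of counselling alone and ban alone against neither, and I the interaction. Counselling changes the outcome by C without the ban and by C + I with it.

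- Counselling main effect = [C + (C + I)]/2 = C + I/2
- Ban main effect = [B + (B + I)]/2 = B + I/2

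With equal cells the additive regression targets the same quantities.

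**4. If each works alone and they are synergistic.** Take alone effects of 0.24 SD and an interaction of 0.48 SD (4 × .12, the stated interaction effect read as f). Aim 1 reports 0.24 + 0.48/2 = 0.48 SD, twice the alone effect. Simulation (138 per cell, 4,000 runs) gives 0.48.

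**5. Worst case: no effect alone, benefit D only when combined.** The main effect is D/2, with SE = √(2/275) = 0.0853 SD. P(significant) ≈ Φ(D/2 ÷ 0.0853 − 1.96).

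| D (SD) | Main effect | P(significant) |
|---|---|---|
| 0.12 | 0.06 | 10% |
| 0.24 | 0.12 | 29% |
| 0.30 | 0.15 | 42% |
| 0.40 | 0.20 | 65% |
| 0.50 | 0.25 | 83% |

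In simulations at D = 0.12, 0.24 and 0.48, the 0/1 coefficients of the interaction model stayed near zero and rejected about 5% of the time. The interaction has SE 4/√550 = 0.1706, twice 0.0853, and here its size is D, twice the main effect. Its power is therefore the same as that of the main effect, so a non-significant interaction is no reliable warning.

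The table applies most directly to counselling, which is randomised within location. For the ban, a test that allows for campus has less power: with an assumed ICC of 0.01 to 0.05, the design effect 1 + (550/16 − 1) × ICC is 1.33 to 2.67, and power at a main effect of 0.24 SD falls from 80% to between 68% and 41%. The I/2 term is unchanged.

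**6. Illustration from the pilot (SSB intake, a secondary outcome).** Combined minus ban only = 25.4 − 8.2 = 17.2 oz/day. Assume no change with neither intervention. Counselling alone (c) was not measured in the pilot, so a range is shown.

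| True c (oz/day) | Counselling main effect (c + 17.2)/2 | Ban main effect (8.2 + 25.4 − c)/2; truth 8.2 |
|---|---|---|
| 0 | 8.6 | 16.8 |
| 8.2 | 12.7 | 12.7 |
| 17.2 | 17.2 | 8.2 |

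In the last row the interaction is zero and nothing is distorted.

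**7. Precision of the alone contrasts.** SE = √(2/138) = 0.1204 SD, which is 1.41 times 0.0853. Detectable d = (1.960 + 0.842) × 0.1204 = 0.337, against 2.802 × 0.0853 = 0.239 for a main effect. Power at d = 0.24 is about 51%. For the ban, each cell has about 138/8 = 17.25 people per campus. With an assumed ICC of 0.01 to 0.05, the design effect 1 + 16.25 × ICC is 1.16 to 1.81, and the detectable d becomes 0.337 × √1.16 = 0.36 to 0.337 × √1.81 = 0.45, before any allowance for having only 8 campuses per arm.

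**The case against.** The plan has several answers.

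- The ANOVA is also meant to compare group means, and Expected Outcomes looks for each of the three exposed groups to improve more than the group with neither. That points towards cell comparisons, but no contrast is specified, and the stated inference rests on main effects and additive coefficients.
- The Aim 2 model already contains the alone effects as its two 0/1 coefficients. This is correct, and it is why the repair is cheap. However, the plan names only the interaction as the target there and breaks it down only when it is significant.
- Main effects are legitimate factorial estimands. They are, as averages over the other factor. They answer a different question from the one Aim 1 poses.

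A reader might go further and infer that Aim 1 must reach a false conclusion if the Aim 2 hypothesis is true, or that Expected Outcomes claims each intervention works alone. The documents support neither. The sponsor expects each intervention to work alone and the two to be synergistic; then the direction is right and only the size is inflated. Section 3 cites four brief-counselling studies that all found declines in SSB intake and/or BMI, and section 2 reports a 4.2 oz/day reduction against controls in the current ban trial. The finding of no benefit from the ban alone concerns employees with strong cravings. The sentence in Expected Outcomes speaks of an effect and does not say alone; a main effect can support it.

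**Conclusion.** The point holds as a mismatch between question and estimate. With equal cells, the Aim 1 coefficients exceed the alone effects by exactly half the interaction, so under the synergy that the plan anticipates they overstate them. A significant result with no alone effect is the worst case and needs an alone effect at or near zero. Its frequency then runs from about 10% to 83% for combined benefits of 0.12 to 0.5 SD. These benefits are assumed, and the rates presume independent errors. With no interaction the distortion vanishes, and with antagonism it reverses. The pilot figures illustrate the mechanism for SSB intake; they do not predict the bias in waist circumference or HOMA.

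**What to change.** - In the Aim 1 Analytic Plan, name as the Aim 1 estimates the two 0/1 coefficients of the interaction model already planned for Aim 2: counselling where ban = 0, and ban where counselling = 0. Report both with confidence intervals whether or not the interaction is significant.
- Keep the four-cell main effects, labelled as effects averaged over the other factor.
- In Aim 1, Expected Outcomes, state that a significant main effect shows an average effect and does not by itself answer the alone question.
- In Aim 1, Power Calculations, add the detectable effect for the alone contrasts and name its scale: about d = 0.34, against 0.24 for main effects at individual level. For the ban, give a figure that allows for randomisation of 8 versus 8 campuses, with the assumed ICC stated.

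Cost: no new data, participants or models. The alone contrasts have standard errors about 1.4 times larger, and power at d = 0.24 is about 51%. Recovering 80% at d = 0.239 would take 275 per cell, twice the plan, so the less favourable figure should be disclosed.
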